5. REPORTING PROCEDURES

ADVERSE EVENTS

Definitions

Where the definition indicates 'device', it refers to any device used in the study. This might be the device under investigation, or any market released component of the system.

AE – Adverse Event: Any untoward medical occurrence unintended disease or injury, or untoward clinical signs (including abnormal laboratory findings) in subjects, users or other persons, whether or not related to the investigational medical device

- This definition includes events related to the IMD
- This definition includes events related to the procedures involved
- For users or other persons, this definition is restricted to events related to IMD (ISO 14155:2011, 3.2)

ADE - Adverse Device Effect : Adverse event related to the use of an IMD

- This definition includes AE resulting from insufficient or inadequate instructions for use, deployment, implantation, installation of operation, or any malfunction of the IMS
- This definition includes AE resulting from an error use or from intentional misuse of the IMD (ISO 14155:2011, 3.1)

٠

DD – Device Deficiency: inadequacy of a MD with respect to its identity, quality, durability reliability, safety or performance.

• Device deficiencies include malfunctions, use errors and inadequate labelling

(ISO 14155:2011, 3.15)

a.

SAE- Serious Adverse Event: Any untoward medical occurrence that:

- Results in death;
- Is life-threatening*;
- Requires in-patient hospitalisation or prolongation of existing hospitalisation**;
- Results in persistent or significant disability or incapacity, or;
- Consists of a congenital anomaly or birth defect;
- Other important medical events***.

*'life-threatening' in the definition of 'serious' refers to an event in which the patient was at risk of death at the time of the event; it does not refer to an event which hypothetically might have caused death if it were more severe.

Hospitalisation is defined as an inpatient admission, regardless of length of stay, even if the hospitalisation is a precautionary measure for continued observation. Hospitalisations for a preexisting condition, including elective procedures that have not worsened, do not constitute an SAE. *Other important medical events that may not result in death, be life-threatening, or require hospitalisation may be considered a serious adverse event/experience when, based upon appropriate medical judgment, they may jeopardise the subject and may require medical or surgical intervention to prevent one of the outcomes listed in this definition.

General

- The MarginProbe is a low-risk device. In previous intended use studies the observed rates for adverse events, including serious adverse events (SAEs), were low and there were no differences observed between the device and the control groups. There were no Probable or Definite device-associated adverse events.
- As is reported in the literature, a significant proportion of patients undergoing lumpectomy procedures are expected to have positive margins and undergo additional breast and axillary procedure(s). Further, some patients are expected to undergo additional breast procedures in the contralateral breast as a result of the workup. Therefore, breast and axillary surgical procedures and hospitalizations are expected to occur in the study population. Thus, breast or axillary procedures, including the associated hospitalization, will **not** be considered as an AE or as a SAE and will not require reporting to authorities.
- Adverse Events (AE) will be followed until the end of the initial lumpectomy procedure. Because adverse events potentially related to the use of the MarginProbe are very limited, and any such events would be likely to arise in the surgery or the immediate postoperative period, only those adverse events observed at surgery or the one month post-study visit will be followed. All such events will be followed until resolution or the final follow-up visit, whichever occurs first.
- Serious Adverse Events (SAE) (as a subset of those AEs defined in (e) above) will be followed until the final (9 month) follow-up visit or resolution of the SAE, whichever occurs first.
- The investigator shall report any SAE or UADE immediately, within 24 hours, to the sponsor. The site should contact the relevant person by telephone to provide the initial notification. For this study, UADEs will include device failure or device malfunction resulting in device not being used during surgery.
- The investigator shall provide a written report by facsimile or mail describing the SAE or UADE to the sponsor.
- Reports relating to the patient's subsequent medical course must be submitted to the sponsor until the event has subsided or, in the case of permanent impairment, until the event stabilizes and the overall clinical outcome has been ascertained.
- The investigator is required to comply with applicable regulations regarding the notification of SAE to the reviewing IRB consistent with any IRB conditions of approval.

Assessment of AE Relationship to Study Proceedure

The investigator's assessment of an AE's relationship to the study device is part of the documentation process, but it is not a factor in determining what is or is not reported in the study. If there is any doubt as to whether a clinical observation is an AE, the event should be reported.

The relationship or association of the study device in causing or contributing to the AE will be characterized as one of the following:

Unrelated - suggests the AE can be attributed to something other than the study device.

Possible - suggests that the association of the AE with the study device is unknown. However, the AE is not reasonably supported by other conditions.

Probable - suggests that a reasonable temporal sequence of the AE with the study device exists and, based upon the investigator's clinical experience, the association of the AE with the study device seems likely.

Definitely - suggests that a definite temporal sequence of the AE with the study device exists.

Device Failures and Malfunctions

All device malfunctions will be documented and reported. Devices that malfunctioned during the procedure will be returned to the sponsor for analysis, after appropriate decontamination per hospital guidelines.

Device Malfunction: A device malfunction is an unexpected change to the device that is contradictory to the labeling and may or may not affect device performance.

Device Failure: A device has failed if it does not perform according to labeling and negatively impacts the treatment while used according to the labeling.

Potential anticipated adverse effects

There are no known anticipated device related AEs or SAEs.

Adverse Event Reporting

Only adverse events **specifically related to the device** should be reported. **Do not** report any complications or side effects commonly associated with cancer and/or chemotherapy e.g. septicaemia, neutropenia, deep vein thrombosis and hospitalisation due to viral illness or complications/ events related to surgical procedure.

All device-related SAEs must be reported immediately by the local Investigator to the Chief Investigator. The site should:

• Either, complete the SAE case report form, signed and dated and send immediately (within 24 hours or the next working day, preferably by fax on [name]) to the sponsor together with relevant treatment forms and anonymised copies of all relevant investigations.

• Or, contact the sponsor by telephone and then send the completed SAE form to the sponsor within the following 24 hours as above.

The form asks for nature of event, date of onset, severity, corrective therapies given, outcome and causality The responsible investigator should sign the causality of the event. Additional information should be sent within 5 days if the event has not resolved at the time of reporting.

The sponsor will notify the Main REC of all UADEs occurring in the trial within 15 days of notification, and will provide the Main REC with an annual report of all SAEs. Investigators should report any SAEs as required by their Main Research Ethics Committee and/or Research & Development Office.

NB. Only adverse events e.g. illness, injury and accident specifically related to the device should be reported.

Any questions concerning adverse event reporting should be directed to the Chief Investigator in the first instance. Please see appendix A for further information.

To report an SAE, an SAE form must be completed and returned **within 24 hours** of the clinician becoming aware of the event.

[contact] for the attention of [name]

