- Additional lumpectomy cavity shaving is performed by the surgeon, as deemed necessary, based on this intraoperative assessment.
- Lumpectomy cavity shavings performed based on visual inspection and palpation shall be documented.

Please see Appendix B for further information about the MarginProbe Device.

MarginProbe Schedule of Assessments

2.1					
			1 month	3 months	9 months
	Baseline/	Operative	post	post	post
Assessment	screening visit	visit	surgery	surgery	surgery
Informed Consent	x				
Eligibility criteria	х				
Demographics	х				
Baseline characteristics	x				
Relevant Medical History	x				
Procedural characteristics		x			
Intraoperative imaging use		x			
Pathology assessment		x			
FACT-B, HADS, EQ5D, SABIS					
Questionnaires	X		X (by post)	X (by post)	X (by post)
Randomisation		x			
Photographic measurements	x				x
Adverse events assessed		x	x		
Health Economic Diaries			X (by post)	X (by post)	X (by post)

NB: Adverse events and Serious Adverse events should be recorded, as appropriate, at all points of contact.

4. Data Analysis and Statistical Considerations

Sample size: The ABS 2011 Audit[1] found the average re-excision rate for DCIS is 30% and that for invasive cancers is 25%. It is estimated that approximately 20% of recruited patients will have DCIS and 80%, invasive cancer. The estimated average re-excision rate for the whole study group is 26%. Specialist Centres are expected to have a slightly lower re-excision rate, if we assume a 25% re-excision rate in the control arm and predict that the device will give a 50% reduction in the re-excision rate (i.e. to 12.5%), it is estimated that 219 patients will be required to be recruited in each group (90% power using a simple chi-square test with continuity correction). It is proposed to recruit 230 per group to allow for drop-out and loss to follow-up.

With this number of patients, the study would have 80% power to detect a 44% relative reduction from 25% to 14% in re-excision rate and a 50% relative reduction from 20% to 10% in re-excision rate.

This number of patients would also lead to 90% power to detect differences in TOI of 4.5 or more between the two groups and 80% power to detect differences in TOI of 3.9 or more (using an estimated SD of 15 from the ALMANAC trial and a simple two-sample t-test with the conventional 5% significance level).

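### The adverse-event rules contradict each other on relatedness and on time window; if the device-only reporting rule is applied, adverse-event data cannot give an unbiased comparison of complications between arms

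*Protocol*

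**What the plan says.** All references are to the protocol.

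On which events count, section 5 (Reporting Procedures) makes four statements:

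- Definitions: an adverse event is any untoward occurrence "whether or not related to the investigational medical device". Events tied to the procedures involved are expressly included.
- General: "The investigator shall report any SAE or UADE immediately, within 24 hours, to the sponsor". No condition on relatedness is attached.
- Assessment of AE Relationship: the investigator's judgement is documented, but "it is not a factor in determining what is or is not reported in the study". Doubtful events are to be reported.
- Adverse Event Reporting: only events tied specifically to the device are to be reported. The list of things not to report ends with "hospitalisation due to viral illness or complications/ events related to surgical procedure". A later note repeats the device-only limit. The matching instruction for serious events reads "All device-related SAEs must be reported immediately by the local Investigator to the Chief Investigator".

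On how long events are captured:

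- General: "Adverse Events (AE) will be followed until the end of the initial lumpectomy procedure". The next sentence says that "only those adverse events observed at surgery or the one month post-study visit will be followed", up to resolution or the final visit. Serious events are followed to resolution or the 9-month visit.
- Schedule of Assessments: adverse events are ticked at the operative visit and at 1 month. The note beneath says "Adverse events and Serious Adverse events should be recorded, as appropriate, at all points of contact".

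**The concern.** A site cannot follow both sets of instructions, and the exclusion falls where the arms could differ. Under MarginProbe Device (Trials Procedures), the surgeon must take more tissue from every surface that the device reads as positive. A harm of that strategy would appear mainly as a complication of surgery, which is what the Adverse Event Reporting text tells sites to leave out.

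Attribution adds a second problem. The Blinding and bias paragraph accepts that the surgical team knows the allocation. If reporting depends on relatedness to the device, that team decides whether an event in a device patient counts. In a control patient the question does not arise. What is ascertained would then depend on the arm.

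The data monitoring committee reviews the data every six months. Section 5 itself relies on earlier studies that found no difference in adverse events between device and control groups. Both uses need events counted in the same way in both arms.

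**Working it through.** The protocol gives no complication rate and no safety figure, so there is no figure of its own to reproduce. The check is mainly a comparison of texts.

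1. **Relatedness.** The Definitions, General and Assessment of AE Relationship texts collect events whatever their relation to the device. The Adverse Event Reporting text collects only device-related ones. Take a wound infection judged unrelated to the device. It meets the definition of an adverse event and, under the relationship text, its unrelatedness is no ground for leaving it out. Under the reporting text it must not be reported. For a serious event, one instruction covers any such event and the other only those related to the device.

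2. **Window.** The first General sentence stops at the end of the operation. The second takes in events seen at 1 month, which matches the ticks in the Schedule of Assessments. The first sentence is therefore the outlier. The note on all points of contact is wider again, but it is qualified and concerns recording rather than follow-up.

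3. **Consequence if the device-only rule is applied.** Intraoperative (General) confines use of the device to patients randomised to it. The console is switched on before randomisation, but the probe is opened only in the device arm. Reportable events in the control arm are then 0 of 230 by construction. In the device arm they equal the complications that the unblinded team attributes to the device. The difference between these two counts does not estimate the difference in complication risk.

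4. **What common recording could show.** This is an illustration only. The input from the protocol is 230 per group (Sample size). The complication rates p are assumptions, taken as equal in both arms.
   - Expected events per arm = 230p.
   - 95% half-width for the risk difference = 1.96 × √(2p(1 − p)/230).
   - p = 2%: 4.6 events per arm; 1.96 × √(0.0392/230) = 0.0256, or ±2.6 points.
   - p = 5%: 11.5 events per arm; 1.96 × √(0.095/230) = 0.0398, or ±4.0 points.
   - p = 10%: 23 events per arm; 1.96 × √(0.18/230) = 0.0548, or ±5.5 points.

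These figures describe precision after the fix. They do not measure the defect.

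**The case against.** The strongest reply is that recording and reporting are different things. The device-only text stands under a heading about reporting and deals mostly with notifying the Chief Investigator, the sponsor and the ethics committee. The Trials Procedures list adverse events at the operative visit for every patient, and the Schedule of Assessments adds 1 month, neither with any restriction by arm. The causality scale in Appendix A includes unrelated and unlikely events, categories of little use if only device-related events are captured. On that reading the CRF already holds events from both arms and only notification is narrow.

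This stands as a possible reading, and it limits the conclusion. A reader might infer that the device-only rule is the one in force, that the control arm contributes no events, and that the trial has no randomised safety comparison. The documents do not support that, because nothing gives the device-only text priority over the others. The reply does not remove the contradiction, however. The protocol never separates recording from reporting, and the relationship text speaks of what is reported in the study while stating the opposite rule.

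It is also fair to say that an excess of wound problems would not be wholly invisible. Length of stay, unplanned clinic visits, GP and nurse contacts, blinded cosmesis and quality of life are collected in both arms. They are indirect and do not replace diagnosed complications.

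Finally, the protocol calls the device low-risk, and the primary endpoint is unaffected. Both points bear on priority, not on whether the texts agree.

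**Conclusion.** The contradiction on relatedness is plain on the face of section 5, and so is the conflict between the two adjacent sentences on the window. The consequence is conditional. If the device-only rule is applied, control patients can contribute no reportable event, complications of the extra excision depend on unblinded attribution, and adverse-event data cannot support an unbiased comparison of complications between arms. If sites instead record under the Schedule of Assessments, the comparison may survive. The protocol leaves that choice to each site, so capture may also differ between sites.

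The conclusion rests on the wording alone. The half-widths of ±4.0 and ±5.5 points depend on assumed complication rates of 5% and 10%. The absence of a named safety analysis is not part of this point, since a statistical analysis plan may supply one. It could not restore events that were never recorded.

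**What to change.** Reconcile the texts into one collection rule that applies identically in both arms:

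- Record adverse events, including surgical complications, on the CRF regardless of relatedness at the operative and 1-month assessments already scheduled, and make them available by randomised arm.
- State that the device-only text under Adverse Event Reporting governs only expedited notification to the sponsor, Chief Investigator and ethics committee, and bring the 24-hour instruction for any serious event into line with it.
- Delete the General sentence that ends follow-up at the lumpectomy, or align it with the next sentence and the Schedule of Assessments.
- Keep the follow-up of serious events to resolution or 9 months as stated. It is a follow-up duration and should not become a new collection window.
- Leave the existing exemption for breast or axillary procedures unchanged.

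The cost is an amendment, CRF wording and modest extra data entry at sites; no assessment is added. One limit remains. The Background puts re-excisions at 5 to 6 weeks after the first operation, so a 1-month assessment mainly covers complications of the first operation.

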5. INFORMED CONSENT, ETHICAL AND REGULATORY CONSIDERATIONS

Ethical Approval

This trial will adhere to the principles outlined in the International Conference on Harmonisation Good Clinical Practice (ICH GCP) guidelines. It will be conducted in compliance with the protocol, GCP, the Data Protection Act and other regulatory requirements, as appropriate.

Multicentre Research Ethics Committee (MREC) approval has been obtained for this trial, and Site Specific Assessments (SSAs) will be performed at participating centres. The trials centre will maintain contact with NRES and will submit any protocol amendments. The trials centre will forward any resulting documentation to local centres.

Patient Informed Consent

The local investigator is required to explain the nature and purpose of the trial to the patient prior to trial entry. A detailed patient information sheet and consent form will be given to the patient and written informed consent obtained before entry to the trial.

Protocol Compliance

MAHSC-CTU data management staff will be in regular contact with local centre personnel to check on progress and to help with any queries that may arise, with regards to data related matters. Incoming forms will be checked for completeness, consistency, timeliness and compliance with the protocol.

The data management team will liaise primarily with the trial project manager to escalate issues, trends and any non-compliance identified by the trial data. The project manager will have an overall view of the study and maintain regular contact with sites. Trial PM is responsible for identifying all relevant protocol deviations that merit recording and actioning, and maintaining oversight of site compliance.

Decisions relating to significant and/or persistent issues with sites are made by the CI//Sponsor, and any issues identified and escalated by the project manager. Centres may be withdrawn from further recruitment in the event of serious and persistent non-compliance.

Data Protection

All data will be kept strictly confidential according to Good Clinical Practice (GCP) Guidelines. At the end of the study, all study data will be stored by the Manchester University NHS Foundation Trust in a secure fashion for 20 years in accordance with the ICH GCP. During the study period, the Case Report Forms will be stored at the MAHSC-CTU.

Source data will be stored at the relevant clinical sites in line with respective Trust policies. Please note, original Questionnaires, diaries and CRF pages are to be sent to be processed; copies of these are to be retained at sites. The trials centre will act to preserve patient confidentiality and will not disclose or reproduce any information by which patients could be identified. Data will be stored in a secure manner and our trials are registered in accordance with the Data Protection Act 1998 with the Data Protection Officer at the relevant NHS Trusts.

Publication Policy

Data from all centres will be analysed together and published as soon as possible after the analysis time point has been achieved; after the last patient has completed their 9 month assessment. Individual participants may not publish data concerning their patients that are directly relevant to questions posed by the trial until the Trial Management Group (TMG) has published its report. The TMG will form the basis of the Writing Committee and advise on the nature of publications.

All publications shall include a list of participants, and if there are named authors, these should include the principal investigator, clinical trial coordinator(s), and statistician(s) involved in the trial and contributors of more than 10% of participants. If there are no named authors then a writing committee will be identified.

TRIAL GOVERNANCE

Independent Data Monitoring and Ethics Committee (IDMC), Independent Trial Steering Committee (TSC) and Trial Management Group (TMG)

The trial will have an IDMC with an independent Chairman. In addition, the Trial Steering Committee includes 2 patient representatives.

The data will be reviewed six monthly by an IDMC, consisting of at least two clinicians not entering patients into the trial and an independent statistician. The IDMC will be asked to recommend whether the accumulated data from the trial, together with results from other relevant trials, justifies continuing recruitment of further patients. The IDMC would make a decision to discontinue recruitment, in all patients or in selected subgroups. However, thiswill be made only if the result is likely to convince a broad range of clinicians including participants in the trial and the general clinical community. If a decision is made to continue, the IDMC will advise on the frequency of future reviews of the data on the basis of accrual and event rates. The IDMC will make confidential recommendations to the TSC.

The role of the TSC is to act on behalf of the funder, to provide overall supervision for the trial, to ensure that it is conducted in accordance with GCP, and to provide advice through its independent Chairman. This independent committee will review the recommendations from the IDMC and will decide on continuing or stopping the trial, or modifying the protocol.

The Trial Management Group, under the chairmanship of the Chief Investigator, will coordinate and manage the trial's day-to-day activities. It will include all of the Grant co-applicants, all of the PIs or

their representatives, the Study Coordinator and representatives from the MAHSC CTU. We currently aim to hold these face-to-face meetings at six monthly intervals.

